6.2.1.3 Durvalumab Administration

Durvalumab infusions are to be administered through an IV administration set with a 0.2 or $0.22~\mu m$ filter; acceptable configurations include an IV set containing an in-line filter or the attachment of a separate filter to the distal end of the IV tubing.

The durvalumab infusion time is 1 hour \pm 10 minutes; however, if there are interruptions, the total allowed time must not exceed 8 hours with the infusion bag maintained at room temperature, otherwise a new dose must be prepared from new vials.

Do not co-administer other drugs through the same infusion line.

The IV line will be flushed according to local practices to ensure the full dose is administered. Infusion time does not include the final flush time.

6.2.2 Ceralasertib Storage and Administration

6.2.2.1 Ceralasertib Storage

Ceralasertib product label on the bottle specifies the appropriate storage. It must be stored in the original outer container and under conditions specified on the label.

6.2.2.2 Ceralasertib Administration

Ceralasertib tablets should be taken with a glass of water. When ceralasertib is administered, patients must fast (water permitted) for at least 2 hours prior to taking a dose, to at least 1 hour post-dose for all doses.

Ceralasertib will be administered orally 240 mg twice daily, approximately 12 ± 2 hours apart, starting on Day 1 until Day 7, in each treatment cycle of both the treatment arms in the main study. In the biopsy sub-study, patients will self-administer ceralasertib tablets from Day 1 until Day 7 of Cycle 0, followed by no study treatment between Day 8 and Day 28, and from Day 1 until Day 7 Cycle 1 onwards.

Patients must receive ceralasertib for 7 days within each 28-day cycle. A cycle must not be < 28 days. Ceralasertib must not be given on any other days of the cycle, and dosing days must stay relative to Day 1 of each cycle. In case of drug interruption within the planned Days 1 to 7 dosing window (for any reason), resumption of treatment can only take place within the planned dosing window and not beyond, even if this means the patient receives less than the specified 7 days of ceralasertib dosing in the particular cycle. Dosing after Cycle Day 7 is not permitted and the planned 21 days off treatment should not be reduced.

Patients are allowed to take the scheduled dose up to 2 hours after the scheduled dose time. If the interval between two doses is more than 14 hours, then the missed dose should not be taken and the patient should continue with the next dose at the allotted time. If the patient wishes to bring forward the time of their scheduled dose, the dose can be taken up to a maximum of 2 hours prior to the scheduled time, ie, \pm 2-hour window.

6.3 Measures to Minimise Bias: Randomisation and Blinding

6.3.1 Main Study

This is an open-label study; potential bias will be reduced by the following steps: central randomisation, use of BICR for tumour assessments and use of IDMC (Section 9.6).

For the main study, patients will be randomly allocated to receive 1 of the study treatments, at a 2:1 randomisation ratio, such that there will be approximately 100 evaluable patients in the ceralasertib and durvalumab combination therapy arm and approximately 50 patients in the ceralasertib monotherapy arm.

At enrolment, Investigators will confirm PD-(L)1 resistance type and whether the LDH is normal or above upper limit of normal in order to stratify the patients accordingly.

Stratification factors include:

- Resistance to prior immune-oncology treatment (primary/early relapse in adjuvant setting vs secondary resistance). Based on SITC (Kluger HM et al, 2020) definitions of resistance to PD-(L)1 therapy:
 - Primary resistance: patients with a drug exposure of ≥ 6 weeks who had PD or stable disease for ≤ 6 months.
 - Secondary resistance: patients with a drug exposure of ≥ 6 months who had confirmed CR or PR, or SD for ≥ 6 months
 - Early relapse in adjuvant setting: patients with PD within 12 weeks of the last dose
- Baseline lactate dehydrogenase expression (below and equal to the upper limit of normal vs above upper limit of normal). Lactate dehydrogenase will be determined by a local test and values can vary depending on the lab. Therefore, patients will be stratified for LDH normal or above upper limit of normal, according to local lab reference ranges.

Patients will be randomised as they become eligible. Once the eligibility of a patient has been confirmed, the investigator (or designee) will notify the centralised IWRS (all patients). The IWRS will then provide the randomisation identification code. Randomisation should take place as close to the start of study treatment as possible (randomisation does not apply to patients in the biopsy sub-study).

Due to the different schedules of administration of the treatment options, neither patients nor investigators will be blinded to treatment assignment. However, to limit bias to study conduct, data quality, data analyses and data interpretation, appropriate key personnel and certain functions at AstraZeneca will remain blinded to treatment allocation until the database lock at primary analysis. Separate unblinded counterparts eg, biostatisticians and statistical programmers will do all necessary unblinded work during the course of the study, including interaction with the IDMC. Detailed procedures for maintenance of the blind will be described in the IDMC Charter and the study integrity plan.

Study treatment details are summarised in Section 6.

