2.2.2 Melanoma

Melanoma is the most serious form of skin cancer and the fifth most frequently diagnosed cancer in the US, with 100,350 new cases estimated to occur in 2020, representing 6% of all new cancer diagnoses. The incidence of melanoma is increasing each year. Five-year survival rates depend on the stage of disease at the time of diagnosis. For those with localised disease, 5-year relative survival is estimated at 92%. However, in the US, approximately 4% of patients present with metastatic melanoma, the main cause of melanoma deaths (Zbytek B et al, 2008), and the 5-year relative survival rate is approximately 25%. In 2020, it is anticipated that there will be an estimated 6,850 deaths from melanoma (Siegel RL et al, 2020).

In the US, since 2011, mortality rates for melanoma have declined rapidly, decreasing by an average of approximately 7% per year between 2013 and 2017. This decline in mortality for metastatic disease has been attributed to the approval of immunotherapies such as CPIs and targeted treatments such as BRAF and MEK inhibitors (Siegel RL et al, 2020). Whilst approximately 50% of patients may be suitable for targeted therapy, immunotherapy is the mainstay of treatment, due to the fact that durable CRs and long-term clinical benefit are observed. However, the majority of patients treated with CPI would exhibit either primary resistance (defined as treatment duration ≥ 6 weeks and best response of progressive disease or stable disease for < 6 months), or secondary resistance (defined as treatment duration \geq 6 months and best response of CR, PR, or stable disease for \geq 6 months), according to Society for Immunotherapy of Cancer consensus definition (Kluger HM et al, 2020). However, when resistance to CPI occurs on treatment, there are no standards of care and the available treatment recommendation options are limited and provide minimal clinical benefit. Chemotherapy may be an option for these patients but has not been proven to increase survival and is associated with a short-lasting objective response in a minority of patients, as reported in few retrospective studies. The majority of these studies pre-date the use of CPI. However, there are retrospective studies which have reported anecdotal activity of chemotherapy in immunotherapy-resistant patients, with varying magnitudes of benefit (Goldinger DS et al, 2018).

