5.1 Inclusion Criteria

5.1.1 Main Study and Biopsy Sub-Study

Patients are eligible to be included in the study only if all of the following criteria apply:

Informed Consent

- 1 Capable of giving signed informed consent as described in Appendix A which includes compliance with the requirements and restrictions listed in the ICF and in this protocol.
- Provision of signed and dated written CCI informed consent prior to collection of samples for CCI that supports CCI

Age

Patient must be ≥ 18 years of age inclusive, at the time of signing the informed consent.

Type of Patient and Disease Characteristics

- 4 Patient must have a histologically or cytologically confirmed diagnosis of unresectable or metastatic melanoma of cutaneous, acral or mucosal subtype.
- Availability of an archival tumour sample and a fresh tumour biopsy taken at screening, if medically feasible as per investigator assessment. If a mandatory fresh biopsy is not feasible, the patient is permitted to enrol if they have an archival sample up to 5 years.
- Patient must have received at least 1 prior immunotherapy (anti-PD-(L)1 ± anti-CTLA-4) for a minimum of 6 weeks and no more than 2 prior regimens in the metastatic setting. Patients must have confirmed progression during treatment with a PD-(L)1 inhibitor +/- a CTLA-4 inhibitor, eg, nivolumab, pembrolizumab, or atezolizumab, or the combination

- of nivolumab and ipilimumab. Confirmed progression is defined as radiologic progression confirmed by a second scan at 4 to 12 weeks after the initial scan showing disease progression or, a single scan showing radiological progression accompanied by correlative symptoms suggestive to disease progression. Patients who received adjuvant therapy for previously resected disease with PD-(L)1 agents may also be eligible if disease recurrence occurred while still receiving the anti-PD-(L)1 therapy or < 12 weeks from the last dose of the anti-PD-(L)1 therapy.
- No intervening treatment eg, investigational therapy is permitted between the anti-PD-(L)1 therapy and study treatment. However, patients with BRAF or c-Kit mutations that are eligible for targeted treatment, may receive the targeted treatment before or after licensed anti-PD-(L)1 therapy and prior to study entry. For country-specific requirements for France see Appendix K 1.2.
- 8 The interval between the last dose of anti-PD-(L)1, BRAF/MEK inhibitor and the first dose of the study regimen must be a minimum of 14 days.

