9.4.2.3 Subgroup Analysis

Subgroup analyses will be conducted, estimating primary and secondary endpoints (ORR, PFS, OS) in the following subgroups (but not limited to):

- Resistance to prior IO treatment (primary / early relapse on adjuvant versus acquired)
- Baseline LDH (<= ULN versus > ULN)
- Resistance to prior IO treatment (primary versus early relapse on adjuvant versus acquired)
- Baseline LDH CCI
- Sex (male versus female)
- Age at randomisation (< 65 years versus >= 65 years of age)
- Melanoma subtype (cutaneous versus acral versus mucosal)
- Presence of liver metastases (yes vs no)
- Presence of brain metastases (yes vs no)

Other baseline variables may also be assessed if there is clinical justification or an imbalance is observed between the treatment groups. The purpose of the subgroup analyses is to assess the consistency of treatment effect across expected prognostic and/or predictive factors.

The subgroup analyses for the stratification factors will be based on the values entered into the IWRS; all other factors will be based on the values recorded on the eCRF, or from the third-party vendor data.

Additional subgroups of interest and analysis methods will be outlined in the SAP.

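### The resistance strata in Section 6.3.1 overlap at exactly 6 months and leave confirmed responders with under 6 months of prior exposure in neither level

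*Protocol*

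**What the plan says.** Section 6.3.1 stratifies randomisation by resistance to prior immunotherapy at two levels: primary resistance or early adjuvant relapse, against secondary resistance. Citing a consensus definition, it gives three components:

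- The primary component reads "Primary resistance: patients with a drug exposure of ≥ 6 weeks who had PD or stable disease for ≤ 6 months", so its limit on stable disease includes the 6-month point.
- For the secondary component, the text is "Secondary resistance: patients with a drug exposure of ≥ 6 months who had confirmed CR or PR, or SD for ≥ 6 months", which also includes the 6-month point and adds its own exposure condition.
- The adjuvant component covers progression no later than 12 weeks after the final dose.

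Section 2.2.2 cites the same consensus with a different limit: "primary resistance (defined as treatment duration ≥ 6 weeks and best response of progressive disease or stable disease for < 6 months". Its secondary definition also requires at least 6 months of treatment, with CR, PR, or SD of at least 6 months as best response.

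Inclusion criterion 6 (Section 5.1.1) asks for "at least 1 prior immunotherapy (anti-PD-(L)1 ± anti-CTLA-4) for a minimum of 6 weeks" and, in the metastatic setting, confirmed progression during PD-(L)1 treatment. It does not restrict the prior best response.

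The investigator confirms the resistance type at enrolment. The factor is then used in:

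- the randomisation lists, one per stratum (6.3.1.2);
- the logistic model comparing ORR between arms (9.4.2.1.2);
- the stratified log-rank and Cox models for PFS, and for OS by the same method (9.4.2.2.3, 9.4.2.2.4);
- the subgroup analyses (9.4.2.3);
- the monitoring and possible capping of enrolment by resistance group (9.5).

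On the source for subgroups, Section 9.4.2.3 states: "The subgroup analyses for the stratification factors will be based on the values entered into the IWRS". All other subgroup factors come from the eCRF or vendor data.

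**The concern.** Stratum levels should place every eligible patient in exactly one cell. These levels fail in both directions: one history fits two levels and another fits none. Because the IWRS needs one of two values and the protocol gives no default, two sites can enter the same history differently.

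At stake are consistent classification, some of the efficiency gained by stratifying, the meaning of the enrolment caps, and the reading of the two-level resistance subgroup. That subgroup exists to show whether effects are consistent across prognostic or predictive factors, and it is harder to interpret if some membership depends on the site. Section 6.3.1 also contradicts Section 2.2.2 on the limit for primary resistance while relying on the same source.

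**Working it through.** The plan states no figure to reproduce here. The check is logical.

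**Rules.** E is exposure to the prior PD-(L)1 regimen, B is best response, and D is duration of stable disease.

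- Primary (6.3.1): E ≥ 6 weeks, and B = PD or (B = SD and D ≤ 6 months).
- Secondary (6.3.1): E ≥ 6 months, and B = confirmed CR/PR or (B = SD and D ≥ 6 months).
- Primary (2.2.2): as in 6.3.1, but with D < 6 months.
- Early relapse: adjuvant setting only.
- Eligibility (5.1.1, metastatic setting): E ≥ 6 weeks and progression on treatment, with any B.

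**Overlap.** Take B = SD, D = 6 months, E ≥ 6 months. Primary holds because 6 ≤ 6, and secondary holds because 6 ≥ 6. Under 2.2.2, primary fails because 6 < 6 is false, so the overlap arises only in 6.3.1.

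**Gap.** Take B = confirmed PR, E = 4 months, metastatic setting, progression on treatment. The patient is eligible. Primary fails because B is neither PD nor SD. Secondary fails because 4 < 6. Early relapse does not apply. The 2.2.2 wording gives the same result, so the gap is present in both sections.

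**Grid check.** Ten exposures were used (1.4, 2, 3, 4, 5, 5.9, 6, 6.1, 8 and 12 months). PD, PR and CR each give 10 profiles. SD, with D no longer than E and drawn from the same ten values, gives 1 + 2 + … + 10 = 55. The total is 3 × 10 + 55 = 85 profiles.

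| Rule | In both levels | In neither level |
|---|---|---|
| 6.3.1 | 4 | 12 |
| 2.2.2 | 0 | 12 |
| Primary = PD or SD < 6 months; secondary = any confirmed CR/PR or SD ≥ 6 months | 0 | 0 |

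The 4 are SD of exactly 6 months at exposures of 6, 6.1, 8 and 12 months. The 12 are CR or PR at the six exposures below 6 months (2 × 6). These are counts of profiles, not patient frequencies.

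**Alternative reading.** The gap depends on reading PD as the best response, as 2.2.2 says explicitly. If PD meant progression at any time, every eligible metastatic-setting patient would be primary, because progression is required for entry. Every secondary patient in that setting would then meet both definitions.

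**Scale.** The documents give no share. As an assumption only, 1% to 10% of 150 randomised patients would be 1.5 to 15 patients.

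**The case against.** The strongest reply is that little depends on this, and much of it stands.

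- **Primary analysis.** It is ORR per arm with Clopper-Pearson intervals. Resistance type does not enter it, and Section 9.1 sets no formal hypotheses.
- **Subgroups.** A reader might infer that every resistance subgroup is tied to the IWRS. Section 9.4.2.3 ties only the stratification factors. The stratification factor has two levels, so the separate three-level split (primary, early adjuvant relapse, acquired) appears already to come from the eCRF. The protocol still gives no rule for placing the unclassified responders there.
- **Size.** A reader might suppose that scan intervals cluster stable-disease durations at 6 months. The protocol gives no scan schedule for prior therapy, so this has no support. The overlap needs exact equality. The gap needs response, confirmation and progression within 6 months. Responders with at least 6 months of exposure are correctly secondary.
- **Origin.** The gap also appears in the consensus wording as 2.2.2 reports it. How the cited source treats early-progressing responders cannot be checked here.
- **Timing.** Recruitment has ended. Rewriting 6.3.1 would change no allocation and would misdescribe how patients were stratified.

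The reply that this belongs in the SAP does not stand. The definitions acted at enrolment, and the protocol itself states them, contradicts one of them and fixes the source of the two-level subgroup.

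**Conclusion.** The point holds as a defect in a stated rule. The strata in 6.3.1 are neither mutually exclusive nor exhaustive, and the primary limit contradicts 2.2.2. Of the two faults, the unclassified responders matter more, since the exact-6-month overlap probably affects few patients. The total affected is unknown and probably small.

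A reader might go further and infer a biased treatment comparison or an unreliable primary result. The documents do not support either. The stratum is set before allocation, so misclassification does not favour an arm, and the primary per-arm ORR does not use the factor. The consequence is limited to inconsistent classification in the stratified models, the enrolment monitoring and the two-level subgroup. The conclusion assumes that best response is meant, as in 2.2.2, and that no tie-break exists outside the protocol. It warrants correction because the factor is used widely and the remedy is cheap.

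**What to change.** Leave the record of how patients were stratified as it is, and keep the IWRS values for the main stratified analyses.

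Before database lock, state one exclusive and exhaustive derivation rule, identified as an analysis rule and not as a description of the randomisation:

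- primary: best response PD, or SD < 6 months, as in 2.2.2;
- secondary: SD ≥ 6 months, or confirmed CR/PR;
- confirmed responders with under 6 months of exposure: explicitly assigned to one level or shown separately;
- early adjuvant relapse: unchanged.

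Derive resistance type centrally from the prior-treatment data that the Schedule of Activities already collects: best response, start and stop dates, and dates of scans showing progression. The footnotes list best response without saying whether confirmation is recorded, so the rule should say how a recorded CR or PR is handled.

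Use the derived variable for both the two-level and three-level resistance subgroups in 9.4.2.3, and run one sensitivity analysis of the stratified ORR, PFS and OS models with it. Report how many patients change level or had no determinate level.

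The cost is one derived variable, a wording change in 9.4.2.3 and one extra analysis. No new data or patients are needed.

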6.3.1.1 Screening Procedures

If a patient withdraws from the study, then his/her enrolment/randomisation code cannot be reused. Withdrawn patients will not be replaced.

Investigators should keep a record (ie, the patient screening log) of patients who entered screening.

At screening/baseline (Days -21 to -1), the investigators or suitably trained delegate will:

- Obtain signed informed consent before any study-specific procedures are performed. If laboratory or imaging procedures were performed for alternate reasons prior to signing consent, these can be used for screening purposes with consent of the patient. However, all screening imaging results must have been obtained within 28 days of randomisation and all screening laboratory results within 21 days of randomisation.
- Identify patients to the IWRS per country regulations. Obtain a unique 7-digit enrolment number (E-code), through the IWRS in the following format (ECCNNXXX: CC being the country code, NN being the centre number, and XXX being the patient enrolment code at the centre). This number is the patient's unique identifier and is used to identify the patient on the eCRFs.
- Determine patient eligibility (see Sections 5.1 and 5.2).
- Obtain signed informed consent for genetic research study (optional). Patients who decide not to sign the specific genetic ICF but the general study ICF are eligible for study enrolment and all other study procedures.

If the patient is ineligible and not randomised, the IWRS should be accessed to terminate the patient in the system.

Patients will begin treatment on Day 1. Treatment should start no more than 3 working days after being randomised. Patients must not be randomised and treated unless all eligibility criteria have been met.

6.3.1.2 Methods for Assigning Treatment Groups

The actual treatment given to patients will be determined by the randomisation scheme in the IWRS. The randomisation scheme will be produced by a computer software programme that incorporates a standard procedure for generating randomisation numbers. One randomisation list will be produced for each of the randomisation strata. A blocked randomisation will be generated, and randomisation will be balanced within the IWRS at the site/country/region/central level. All centres will use the same list in order to minimise any imbalance in the number of patients assigned to each treatment group.

Randomisation codes will be assigned strictly sequentially, within each stratum and site/country/region, as patients become eligible for randomisation. The IWRS will provide the kit identification number to be allocated to the patient at the randomisation visit and subsequent treatment visits.

6.3.1.3 Procedures for Handling Incorrectly Enrolled or Randomised Patients

Patients who fail to meet the eligibility criteria should not, under any circumstances, be enrolled or receive study medication. There can be no exceptions to this rule. Patients who are

enrolled but subsequently found not to meet all the eligibility criteria must not be randomised or started on study treatment and must be withdrawn from the study.

Where a patient does not meet all the eligibility criteria but is randomised in error, or incorrectly started on treatment, the investigator should inform the AstraZeneca study clinical lead immediately, and a discussion should occur between the AstraZeneca study clinical lead and the investigator regarding whether to continue or discontinue the patient from treatment. The AstraZeneca study clinical lead must ensure all decisions are appropriately documented and that the potential benefit/risk profile remains positive for the patient.

